7.1.2.5 Visit 12 (Week 52) - amended

This is the last visit of the main treatment phase, and the first visit of the long-term extension phase. At this visit, the patient should attend the clinic without having taken the morning dose of riociguat or placebo.

Before intake of study medication:

- Questionnaires (see Section 7.6.13)
- Smoking history
- Physical examination, including weight (Note: BMI will be calculated automatically in the eCRF)

- Oxygen saturation will be measured before and after intake of study drug (see Section 7.6.18, Table 7–2, Table 7–3, and Table 7–4).⁸⁰
- Vital signs (blood pressure and heart rate). Blood pressure and heart rate will be measured at all visits with the patient in a sitting position, after the patient has been at rest for at least 5 minutes. The same arm is always used for these measurements (see Section 7.6.5)
- Assessment of orthostatic changes: measure blood pressure and heart rate in supine position and sitting position approximately 2 h after intake of study drug (see Section 7.6.5).⁸¹
- mRSS (see Section 7.6.6)
- Digital ulcer net burden assessment (see Section 7.6.9)
- Patient’s and physician’s global assessment (see Section 7.6.15)
- Patient interference with skin assessment (see Section 7.6.16)
- Tender and swollen joint count assessment (see Section 7.6.14)
- Blood samples for safety (see Section 7.6.2)
- Pregnancy test (urine) for all women of childbearing potential (see Section 7.6.1)
- 12-lead ECG for centralized reading. A standard 12-lead ECG will be obtained with the patient in the supine position after resting for at least 5 minutes (see Section 7.6.7)
- Pulmonary function tests (FVC and DL_{CO}) (see Section 7.6.8)
- Recording and assessment of AEs (see Section 7.5)
- Concomitant therapy
- Drug accountability
- Start of long-term extension phase
- Assignment of patients to treatment with riociguat via IxRS, dispensation of study drug and intake by patient

After intake of study medication:

- Blood sample for PK (see Section 7.4)
 - PK blood sample between 1 – 2 hours after administration of the morning (first) dose of study medication
 - PK blood sample between 3 – 4 hours after administration of the morning (first) dose of study medication
- Vital signs (blood pressure and heart rate) should be measured within 20 minutes prior to each PK sampling with the patient in a sitting position and after the patient has been at rest for at least 5 minutes. The same arm is always used for these measurements (see Section 7.6.5).

⁸⁰ Per Amendment 6

⁸¹ Per Amendment 6

7.1.2.6 Visits 13 through to 17 – Long-term extension phase - Dose-titration period - amended

At these study visits, the patient should attend the clinic without having taken the morning dose of riociguat.

During the double-blind dose-titration period of the long-term extension phase, the following assessments will be performed according to the Schedule of evaluations (Section 7.1.1):

- Oxygen saturation will be measured before and after intake of study drug (see Section 7.6.18, Table 7–2, Table 7–3, and Table 7–4)⁸²
- Vital signs (blood pressure and heart rate). Blood pressure and heart rate will be measured at all visits with the patient in a sitting position, after the patient has been at rest for at least 5 minutes. The same arm is always used for these measurements (see Section 7.6.5)
- Assessment of orthostatic changes: measure blood pressure and heart rate in supine position and sitting position approximately 2 h after intake of study drug (see Section 7.6.5).⁸³
- Digital ulcer net burden assessment (see Section 7.6.10)
- Blood samples for safety (Visit 17; see Section 7.6.2)
- Blood sample for PK up to 1 hour before the morning dose of study drug (see Section 7.4)
- Pregnancy test (urine) for all women of childbearing potential (on-site at Visits 14 and 16) (see Section 7.6.1)
- Recording and assessment of AEs (see Section 7.5)
- Concomitant therapy
- Dose titration according to the titration algorithm (see Section 4.1.2)
- Dispensation of study drug and drug accountability

7.1.2.7 Visits 18 through Visit n (every 12 weeks) – Long-term extension phase – Open-label extension period - amended

At these study visits, the patient should attend the clinic without having taken the morning dose of riociguat.

During the open-label extension period, the following assessments and procedures will be performed according to the Schedule of evaluations (Section 7.1.1):

- Questionnaires (see Section 7.6.13)
- Smoking history
- Physical examination, including weight

⁸² Per Amendment 6

⁸³ Per Amendment 6

- Oxygen saturation measurement using forehead pulse oximetry (see Section 7.6.18).⁸⁴
- Vital signs (blood pressure and heart rate). Blood pressure and heart rate will be measured at all visits with the patient in a sitting position, after the patient has been at rest for at least 5 minutes. The same arm is always used for these measurements (see Section 7.6.5)
- mRSS (see Section 7.6.6)
- Digital ulcer net burden assessment (see Section 7.6.10)
- Blood samples for safety (see Section 7.6.2)
- Pregnancy test (urine) for all women of childbearing potential (every 4 weeks) (see Section 7.6.1). When pregnancy testing coincides with a visit, the test should be performed at the site, but otherwise should be performed at home.
- 12-lead ECG for centralized reading. A standard 12-lead ECG will be obtained with the patient in the supine position after resting for at least 5 minutes (see Section 7.6.7)
- Pulmonary function tests (FVC and DL_{CO}) (see Section 7.6.8)
- Recording and assessment of AEs (see Section 7.5)
- Concomitant therapy
- Dispensation of study drug and drug accountability

7.1.2.8 Termination Visit - amended

The termination visit will be performed if the patient is discontinued⁸⁵ from study medication for any reason except death or lost to follow-up, and should occur as soon as possible after the patient receives his/her last dose of study drug. Assessments and procedures at this visit include the following:

- Questionnaires (see Section 7.6.13)
- Smoking history
- Physical examination, including weight
- Oxygen saturation measurement using forehead pulse oximetry (see Section 7.6.18).⁸⁶
- Vital signs (blood pressure and heart rate). Blood pressure and heart rate will be measured at all visits with the patient in a sitting position, after the patient has been at rest for at least 5 minutes. The same arm is always used for these measurements (see Section 7.6.5)
- mRSS (see Section 7.6.6)
- Digital ulcer net burden assessment (see Section 7.6.10)
- Tender and swollen joint count assessment (not needed after V12, see Section 7.6.14)⁸⁷

⁸⁴ Per Amendment 6

⁸⁵ Per Amendment 4

⁸⁶ Per Amendment 6

- Patient's and physician's global assessment (not needed after V12⁸⁸, see Section 7.6.15)
- Patient interference with skin assessment (not needed after V12⁸⁹, see Section 7.6.16)
- Blood samples for safety (see Section 7.6.2)
- Pulmonary function tests (FVC and DL_{CO}) (see Section 7.6.8)
- Blood sample for biomarkers (if TV occurs before Visit 8) (see Section 7.6.3)
- Skin biopsy (if TV occurs before Visit 8) (see Section 7.6.9)
- Pregnancy test (urine) for all women of childbearing potential (if 4 weeks since the previous visit) (see Section 7.6.1)
- 12-lead ECG for centralized reading. A standard 12-lead ECG will be obtained with the patient in the supine position after resting for at least 5 minutes (see Section 7.6.7)
- Recording and assessment of AEs (see Section 7.5)
- Drug accountability
- Concomitant therapy

See also Section 7.1.2.10 for further planned assessments.

7.1.2.9 Safety follow-up visit - amended

Patients must be evaluated for safety 30 (+ 5) days after the last dose intake of study medication. Assessments will include the following:

- Physical examination, including weight
- Oxygen saturation measurement using forehead pulse oximetry (see Section 7.6.18).⁹⁰
- Vital signs (blood pressure and heart rate). Blood pressure and heart rate will be measured at all visits with the patient in a sitting position, after the patient has been at rest for at least 5 minutes. The same arm is always used for these measurements (see Section 7.6.5)
- Recording and assessment of AEs (see Section 7.5)
- Blood samples for safety (see Section 7.6.2)
- Pregnancy test (urine) for all women of childbearing potential
- 12-lead ECG for centralized reading. A standard 12-lead ECG will be obtained with the patient in the supine position after resting for at least 5 minutes (see Section 7.6.7)
- Concomitant therapy
- Survival status (see Section 5.2.1)

⁸⁷ Per Amendment 1

⁸⁸ Per Amendment 1

⁸⁹ Per Amendment 1

⁹⁰ Per Amendment 6

7.1.2.10 Premature discontinuation of study drug treatment - amended

In the event of premature discontinuation of study drug treatment, patients must undergo the same procedures as outlined for the termination visit (Section 7.1.2.8) and then undergo evaluation at the safety follow-up visit, 30 (+5) days later (Section 7.1.2.9).

The reason for premature discontinuation of study drug treatment or early withdrawal from the study must be recorded in the eCRF (please refer to Section 5.2).

If the patient discontinues study drug⁹¹ prematurely during the main treatment phase (Week 0 – Week 52) he/she will be invited to come for limited assessments (mRSS, pulmonary function test [FVC and DL_{CO} including hemoglobin measurement at the local laboratory]⁹², PROs, and patient's and physician's global assessment)⁹³ at Week 12, Week 26, Week 39 and Week 52, depending on the timing of discontinuation⁹⁴. This will be in addition to the termination visit assessments (see Section 7.1.2.8), provided that the patient does not object to collection of study data after withdrawal of consent. If the discontinuation occurs before Visit 8 (Week 14), a skin biopsy will also be performed.

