- Vital status (at Week 52)
- Outcome of serious adverse events (SAEs)
- Efficacy endpoints at Weeks 12, 26, 39, and 52 (depending on timing of discontinuation of study medication)

The information should be collected in the eCRF until the safety follow-up visit 30 (+5) days after the last intake of study drug. Serious adverse events that occur within 30 (+5) days after the last dose of study drug will be followed up until resolution, if possible.

If patients refuse to be contacted via telephone (eg, patient objects to further release of information or are lost to follow-up), every effort should be made to obtain vital status (dead or alive) information at Week 52 through consultation of public databases, wherever allowed by local regulations⁴⁸.

The measures taken for follow up must be documented in the site medical record. Follow-up data will be collected for all randomized patients except those who specifically withdraw consent for release of such information, except as noted above. Thus, it is imperative to obtain complete data for all randomized patients, including information on efficacy and safety endpoint events, whether or not they receive study drug, or discontinue study drug prematurely.

Details for the premature termination of the study as a whole (or components thereof [eg, centers, treatment arms, dose steps]) are provided in Section 10.

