7.5.1.3 Assessments and documentation of adverse events

The investigator has the obligation to report AEs. All non-serious events will be assessed and recorded during the specified observational phase (from signing the informed consent form up to the follow-up visit 30 (+5) days after last study medication intake), whether believed to be related or unrelated to the treatment. AE forms will be included in the eCRFs. The record will include clinical symptoms or final diagnosis when available, date of appearance, duration, severity and relationship to treatment. A record will also be kept of the action taken and the follow-up until resolution of the AE.

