7.5.1.4 Reporting of serious adverse events

The definition of SAEs is given in Section [7.5.1.1](#).

Investigator's notification of the sponsor

All investigators will be thoroughly instructed and trained on all relevant aspects of the investigator's reporting obligations for SAEs. This information, including all relevant contact

details, is summarized in the investigator site file. This information will be updated as needed.

All SAEs occurring during the observation period defined in Section 7.5.1.3 must immediately (within 24 hours of the investigator's awareness) be reported to the recipient detailed in the manual. An SAE form must also be completed within 24 hours of the investigator awareness and forwarded to the designated recipient. Each SAE must be followed up until resolution or stabilization by submission of updated reports to the designated recipient.

SAEs occurring after the protocol-defined observation period will be processed by the sponsor according to all applicable regulations.

Notification of the IECs / IRBs

Notification of the IECs / IRBs about all relevant events (eg, SAEs, suspected, unexpected, serious adverse reactions [SUSARs]) will be performed by the sponsor and/or by the investigator according to all applicable regulations.

Notification of the authorities

The processing and reporting of all relevant events (eg, SAEs, SUSARs) to the authorities will be done by the sponsor according to all applicable regulations.

Sponsor's notification of the investigational site

The sponsor will inform all investigational sites about reported relevant events (eg, SUSARs) according to all applicable regulations.

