In Step 1, a patient is clinically evaluated to determine whether the patient has improved or not. Expert consensus on the definition of a patient who is not improved during a trial is the following:

A patient is considered not improved and is assigned a probability score of improving equal to 0.0, irrespective of improvement on other core items, if he/she develops:

1. New scleroderma renal crisis,
2. Decline in FVC % predicted $\geq 15\%$ (relative), confirmed by another FVC % within a month, high resolution computed tomography (HRCT) to confirm interstitial lung disease (if previous HRCT did not show interstitial lung disease) and FVC % predicted below 80% predicted (attributable to SSc),
3. New onset of left ventricular failure (defined as ejection fraction $\leq 45\%$) or new onset of pulmonary arterial hypertension requiring treatment (attributable to SSc).

If the patient is determined to exhibit improvement in Step 1 (ie, not assigned a 0.0), Step 2 involves computing the predicted probability of improving (a score between 0.0 and 1.0, inclusive) for each patient using the equation:

$$\frac{\exp[-5.54 - 0.81 * \Delta_{MRSS} + 0.21 * \Delta_{FVC\%} - 0.40 * \Delta_{Pt-glob} - 0.44 * \Delta_{MD-glob} - 3.41 * \Delta_{HAQ-DI}]}{1 + \exp[-5.54 - 0.81 * \Delta_{MRSS} + 0.21 * \Delta_{FVC\%} - 0.40 * \Delta_{Pt-glob} - 0.44 * \Delta_{MD-glob} - 3.41 * \Delta_{HAQ-DI}]}$$

where Δ_{MRSS} indicates the change in mRSS from baseline to Week 52, Δ_{FVC} denotes the change in FVC % predicted from baseline to Week 52, $\Delta_{Pt-glob}$ indicates the change in patient global assessment, $\Delta_{MD-glob}$ denotes the change in physician global assessment, and Δ_{HAQ-DI} is the change in HAQ-DI¹³¹. Note that all changes are absolute changes ($Time_2 - Time_{baseline}$) and that the physician's and patient's global assessment was measured on the Likert scale ranging from 0 to 10, where 0 = excellent, and 10 = extremely poor.

Hence, the CRISS is comprised of 5 variables: mRSS, FVC % predicted, patient's global assessment, physician's global assessment, and HAQ-DI from the SHAQ patient reported outcome. Combined, the 5 variables explained 89.3% of the variability in the data.

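### Endpoint events are required from patients who stop study drug early, but no listed visit item or reporting window collects them between about 30 to 35 days after the last dose and Week 52

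*Protocol*

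**What the plan says.** Three protocol sections (4.1.5, 5.2.1.3 and 7.1.2.10) describe the visits at Weeks 12, 26, 39 and 52 for a patient who stops study drug early in the main phase: "he/she will be invited to come for limited assessments (mRSS, pulmonary function test". The rest of each list is DLco with a local hemoglobin, the PROs and the two global assessments. AE recording and concomitant therapy are not on it. Both are on the lists for the termination visit (7.1.2.8) and the safety follow-up visit (7.1.2.9).

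Section 7.5.1.3 sets the AE observation period as "from signing the informed consent form up to the follow-up visit 30 (+5) days after last study medication intake". Section 7.5.1.4 uses the same period for serious events: "All SAEs occurring during the observation period defined in Section 7.5.1.3 must immediately". Of later events it says only: "SAEs occurring after the protocol-defined observation period will be processed by the sponsor according to all applicable regulations".

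Section 5.2.1.3 states the opposite intent. It calls for complete data on all randomized patients, "including information on efficacy and safety endpoint events, whether or not they receive study drug, or discontinue study drug prematurely". For patients who withdraw, it lists vital status at Week 52 and "Efficacy endpoints at Weeks 12, 26, 39, and 52 (depending on timing of discontinuation of study medication"), yet the next paragraph says: "The information should be collected in the eCRF until the safety follow-up visit 30 (+5) days" after the last intake.

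Two analyses in Section 8.4.2.2 need these events. CRISS Step 1 overrides the score when a listed event occurs: "A patient is considered not improved and is assigned a probability score of improving equal to 0.0". The adjudicated clinical outcomes are compared between arms by log-rank test.

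**The concern.** A site that follows the visit lists and the reporting window would meet its obligations and still not be asked about organ events in a patient who stopped drug early. Length of event follow-up would then depend on how long the patient stayed on drug.

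Stopping is not random. Section 5.2.1.2 links it to tolerability, and permits it for FVC decline or skin worsening. Patients who stop for progression may be those at higher risk of an organ event, and tolerability-related stopping may differ between arms. Ending their event follow-up soon after the last dose could therefore make censoring in the log-rank comparison informative. The primary mRSS analysis, by contrast, uses all assessments to Week 52.

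For CRISS, the first secondary endpoint in the testing hierarchy, a missed Step 1 event means the patient is scored by the Step 2 equation instead of receiving 0.0.

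A smaller point concerns treatment. Section 6.8 leaves therapy after discontinuation to the investigator, and mRSS values from the limited visits enter the primary model, but the visit list does not ask which immunosuppressants were started. Section 8.4.2.1 plans a sensitivity model that adjusts for time on rescue medication. Rescue is defined in Section 6.9 as an addition to randomized medication, so whether off-drug use counts is not stated.

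**Working it through.** The plan gives no figure for this point, so the check is a comparison of lists, a date calculation and a look at the CRISS equation.

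**1. What is collected off drug, to Week 52**

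| Item | Listed collection after the safety follow-up visit |
|---|---|
| CRISS Step 1 item 1: renal crisis | None |
| CRISS Step 1 item 2: FVC decline | FVC measured at limited visits; repeat FVC and HRCT confirmation not listed |
| CRISS Step 1 item 3: left ventricular failure, new PAH | None |
| Adjudicated cardiac, gastrointestinal and digital outcomes | None |
| Death | Vital status sought at Week 52; all deaths adjudicated |
| CRISS Step 2 components | All five measured at limited visits |

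Where Step 2 components are missing, Section 8.4.2.2 estimates them by MMRM. It has no rule for Step 1 status that was not observed.

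**2. Length of the gap**

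Inputs: Week 52 is Day 364 (Table 7-1); recording ends 30 to 35 days after the last dose (7.5.1.3). For a last dose in week w:

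gap in weeks = [364 − (7w + 30 to 35)] / 7, not below zero.

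| Last dose | Recording ends (day) | Gap to Week 52 (weeks) |
|---|---|---|
| Week 4 | 58 to 63 | 43.0 to 43.7 |
| Week 10 | 100 to 105 | 37.0 to 37.7 |
| Week 26 | 212 to 217 | 21.0 to 21.7 |
| Week 39 | 303 to 308 | 8.0 to 8.7 |
| Week 47 | 359 to 364 | 0 to 0.7 |
| Week 48 | 366 to 371 | none |

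**3. What a missed Step 1 event does to CRISS**

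With no change in any component, the equation in Section 8.4.2.2 gives exp(−5.54) / (1 + exp(−5.54)) = 0.004, which is already classed as not improved. To reach 0.60 the linear predictor must equal ln(0.60/0.40) = 0.405. Through mRSS alone this takes a fall of (5.54 + 0.405) / 0.81 = 7.3 points, so 8 whole points, or an equivalent combination across components. Responder status is wrong only for a patient who stopped drug, had an unrecorded Step 1 event and still improved that much.

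**4. Possible number of missed events**

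The documents give neither a discontinuation rate nor an event rate, so this is illustration only. Take 64 patients per arm (Table 8-2, 80% power), assume 10% to 30% stop early, and assume 2% to 10% of those have a Step 1 event in the gap:

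- low: 64 × 0.10 × 0.02 = 0.13 events per arm
- high: 64 × 0.30 × 0.10 = 1.92 events per arm

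That is about 0.1 to 1.9 per arm, before asking whether a missed event changes responder status.

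**The case against.** The strongest reply is that the requirement already exists. Section 5.2.1.3 treats endpoint events as essential whatever the drug status. It also asks for efficacy endpoints at the four visits; Section 8.3 takes the efficacy variables from Section 7.3, which includes the adjudicated outcomes. Section 7.5.1.5 says these events are captured in the eCRF and adjudicated. The adjudication charter, the eCRF and the main-phase SAP (version 4.0) are not among the documents, so a collection route may be described there.

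This has force. A reader might infer that these events are simply unobserved to Week 52 once drug is stopped. The documents do not support that: the intent to collect is explicit, FVC is measured at the limited visits and vital status is sought at Week 52. Nor can it be shown that AE and SAE forms are the only route into the database. What stands is that no visit list or reporting window in the protocol implements the intent, and that the eCRF sentence in Section 5.2.1.3 pulls against it for withdrawn patients. A SAP can say how unobserved status is scored or censored, but cannot supply events that were never collected.

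A reader might also infer that CRISS becomes an on-drug endpoint. It does not. Step 2 uses off-drug values from the limited visits or MMRM estimates. The dependence on drug status is confined to Step 1 items 1 and 3 and the confirmation of item 2.

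**Conclusion.** The protocol is inconsistent with itself: it requires endpoint events after drug is stopped, but its visit lists and AE/SAE window provide no collection point for most of them. The gap affects patients whose last dose falls before about Week 47 to 48, and it is longest for those who stop during titration.

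The main consequence is possible informative censoring in the log-rank analysis of the adjudicated outcomes. The effect on the CRISS responder comparison is likely small, because an unimproved patient scores close to zero with or without the Step 1 override. Neither effect can be sized, since both depend on unknown discontinuation and event rates. The conclusion also assumes that the unseen charter, eCRF and main-phase SAP add no separate collection route. It is worth correcting because the remedy is cheap, but it does not threaten the primary endpoint.

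**What to change.** Reconcile Sections 4.1.5, 5.2.1.3, 7.1.2.10, 7.5.1.3 and 7.5.1.4:

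- At each limited visit, add a query covering the time since last contact for the CRISS Step 1 events (including the repeat FVC and HRCT result, where done) and the adjudicated outcomes. Forward positive answers to the Adjudication Committee.
- At the same visits, record any immunosuppressive therapy started.
- Run recording of these named events to Week 52 whatever the drug status, and align the eCRF sentence in Section 5.2.1.3. Other AEs can keep the 30 (+5) day limit.
- State how Step 1 status is set when it was not observed.

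This needs no new visit or procedure. The cost is slightly more data entry at sites and a few more cases to adjudicate.

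Amendment 7 was prepared from the main-phase results, so for this version the main-phase visits have probably passed. In that case the study report should give event follow-up time by arm, separately from mRSS follow-up, and state how unobserved Step 1 status was handled.
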